6.2. Background Characteristics

6.2.1. Subject Disposition

The number and percentage of subjects in the following categories will be summarized by flavivirus serostatus and vaccination group as defined in Section 6.1 based on Randomized Set:

- Randomized Set
- Solicited Safety Set
- Safety Set
- Full Analysis Set
- Per-Protocol Set

The percentage will be based on subjects in that vaccination group within the Randomization Set (as randomized), except the Solicited Safety Set and Safety Set for which the percentages will be based on the vaccination group in the Safety Set (as treated).

The number of subjects in the following categories will be summarized based on subjects screened:

- Number of subjects screened
- Number and percentage of screen failure subjects and the reason for screen failure

The percentage of subjects who screen failed will be based on the number of subjects screened. The reason for screen failure will be based on the number of subjects who screen failed.

The number and percentage of subjects in each of the following disposition categories will be summarized by baseline flavivirus serostatus and vaccination group based on the Randomized Set, except otherwise specified:

- Randomized by site
- Received each dose of IP
- Prematurely discontinued before receiving the second dose of IP and the reason for discontinuation
- Completed the main study (c.f. Section 4.1, i.e. the period up to Day 196 visit)
- Prematurely discontinued from the main study and the reason for discontinuation
- Continued into the extension period
- Completed the extension period (percentage based on participants who consent to enter the extension period in the Randomized Set)
- Prematurely discontinued from the extention period and the reason for discontinuation (percentage based on participants who consent to enter the extension period in the Randomized Set)

A subject disposition listing will be provided, including informed consent, subjects who completed the study injection schedule, subjects who completed study, subjects who discontinued from study vaccine or who discontinued from participation in the study, with reasons for discontinuation. A separate listing will be provided for screen failure subjects with reasons for screen failure.

Participants who do not consent to continue into the Extension Period will be considered to have completed the study if they have completed the EOS Visit approximately 6 months (Visit 10 [Day 196]) after the last IP injection. Participants who consent to continue into the Extension Period will be considered to have completed the study if they have completed the EOS Visit approximately 24 months (Day 700) after the last IP injection.

6.2.2. Demographics

Descriptive statistics will be calculated for the following continuous demographic and baseline characteristics: age (years), age group (>=18 and < 50 years, >= 50 and <=65 years), weight (kg), height (cm), and body mass index (BMI) (kg/m²). Number and percentage of subjects will be provided for categorical variables such as gender, race, ethnicity, region and flavivirus serostatus at baseline. The summaries will be presented by flavivirus serostatus and vaccination group as defined in Section 6.1 based on the Safety Set, FAS, and PP Set. If the Safety Set differs from the Randomized Set (e.g., subjects randomized but not received any study injection; subjects received study vaccination other than the vaccination group they were randomized to), the analysis will also be conducted using the Randomized Set.

For screened failure subjects, age (years), as well as gender, race, ethnicity will be presented in a listing.

In addition, subjects with any inclusion and exclusion criteria violation will also be provided in a listing.

6.2.3. Medical History

Medical history data will be coded by system organ class (SOC) and preferred term (PT) using the Medical Dictionary for Regulatory Activities (MedDRA).

The number and percentage of participants with any medical history will be summarized by SOC and PT based on the Safety Set. A participant will be counted only once for multiple events within each SOC and PT. SOC will be displayed in internationally agreed order. PT will be displayed in descending order of frequency of mRNA-1893 Total group and then alphabetically within SOC.

Medical history data will be presented in a listing.

6.2.4. Prior and Concomitant Medications

Prior and concomitant medications and non-study vaccination will be coded using the World Health Organization (WHO) drug dictionary (WHODD). The summary of concomitant medications will be based on the Safety Set. Categorization of prior, concomitant, and post medications is summarized in Appendix C Table 4.

The number and percentage of subjects using concomitant medications and non-study vaccination during the 7-day follow-up period (i.e., on the day of injection and the 6

subsequent days) and during the 28 day follow-up period after each injection (i.e., on the day of injection and the 27 subsequent days) will be summarized by flavivirus serostatus and vaccination group as defined in Section 6.1 as follows:

- Any concomitant medications and non-study vaccination within 7 Days Post Injection
- Any concomitant medications and non-study vaccination within 28 Days Post Injection
- Antipyretic or analgesic medication within 28 Days Post Injection

A summary table of concomitant medications and non-study vaccination that continued or newly received at or after the first injection through 28 days after the last injection will be provided by PT in descending frequency in the mRNA-1893 group with all dose level combined.

Medications taken to prevent pain or fever will be collected on eDiary and summaries will be provided based on the Solicited Safety Set by flavivirus serostatus and vaccination group as defined in Section 6.1 for each injection (first or second) and any injection, including within 7 days after injection.

Prior, concomitant and post medications and non-study vaccination will be presented in a listing.

Concomitant Procedures will be presented in a listing.

6.2.5. Study Exposure

Study IP administration data will be presented in a listing.

Study duration will be summarized since randomization, since the first injection, and since the second injection until complete/discontinued the study or the data cutoff date, whichever occurs first, based on the Safety Set.

6.2.6. Major Protocol Deviations

Major protocol deviations are a subset of protocol deviations that may significantly impact the completeness, accuracy, or reliability of the study data or that may significantly affect a subject's rights, safety, or well-being. Major protocol deviations rules will be developed and finalized before database lock.

The number and percentage of the subjects with each major protocol deviation type will be provided by flavivirus serostatus and vaccination group as defined in Section 6.1 based on the Randomized Set.

Major protocol deviations will be presented in a listing.

6.2.7. COVID-19 Impact

A listing will be provided for COVID-19 impact.

6.3. Safety Analysis

Safety and reactogenicity will be assessed by clinical review of all relevant parameters including solicited ARs (local and systemic), unsolicited AEs, SAEs, AESIs, MAAEs, AEs leading to withdrawal from study vaccine and/or study participation, vital signs, and physical examination findings.

All safety analyses will be based on the Safety Set, except summaries of solicited ARs which will be based on the Solicited Safety Set. All safety analyses will be provided by baseline flavivirus serostatus and vaccination group unless otherwise specified. Subgroup analysis based on age group (>=18 and < 50 years, >= 50 and <=65 years) may be performed.

6.3.1. Adverse Events

An AE is defined as any untoward medical occurrence in a subject or clinical investigation subject who is administered a pharmaceutical product at any dose that does not necessarily have to have a causal relationship with the treatment.

A treatment-emergent AE (TEAE) is defined as any event occurring during the study not before exposure to study vaccine or any event already present that worsens after exposure to study vaccine. Adverse events will also be evaluated by the investigator for the coexistence of MAAE which is defined as an AE that leads to an unscheduled visit to a healthcare practitioner.

Unsolicited AEs will be coded by PT and SOC using MedDRA summarized by baseline flavivirus serostatus, vaccination group, and stage (up to 28 days after each vaccination, up to 28 days after any vaccination and overall stage; see Section 6.1 for definitions of vaccination group and stage).

All summary tables (except for the overall summary of AEs) for unsolicited AEs will be presented by SOC and PT for TEAEs with counts of subjects included. SOC will be displayed in internationally agreed order. PT will be displayed in descending order of frequency of total mRNA-1893 and then alphabetically within SOC. When summarizing the number and percentage of subjects with an event, subjects with multiple occurrences of the same AE or a continuing AE will be counted once. Subjects will be presented according to the highest severity (the strongest relationship) in the summaries by severity (of related AEs), if subjects reported multiple events under the same SOC and/or PT.

Percentages will be based upon the number of subjects in the Safety Set within each vaccination group.

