8.5. Safety Assessments

The planned time points for all safety assessments are provided in Table 1 and Table 2.

Safety assessments will include monitoring and recording of the following for each participant:

• Solicited local and systemic ARs (Section 11.2.3; Appendix 2) that occur during the 7 days following each IP injection (ie, the day of injection and 6 subsequent days). Solicited ARs will be recorded daily using eDiaries (Section 8.5.1).

Additional blood collections may be required at the discretion of the investigator to follow-up on abnormal results.

Peripheral blood mononuclear cells will be isolated from blood samples collected from the CMI subset participants, which is a subset of participants selected from approximately 4 sites that have experience in human cell collection.

The approximate blood volume of 300 mL includes the volume collected for the PBMC collection and the other assays in the CMI subset participants over a period of 18 months with a 6-month periodicity; for the other participants, the blood volume collected is approximately 36 mL.

In case of signs or symptoms suggesting a flavivirus infection (mostly dengue and Zika in the areas where the study will be performed), an additional blood sample will be collected to confirm the diagnosis via specific serology and RT-PCR.

Unsolicited AEs observed or reported during the 28 days following each IP injection (ie, the day of injection and 27 subsequent days). Unsolicited AEs are AEs that are not included in the protocol-defined solicited ARs (Section 11.2.3; Appendix 2). Unsolicited AEs will be captured during safety telephone calls or at site visits and recorded on the participant's AE CRF.

- AEs leading to discontinuation from IP and/or study participation throughout the entire study duration (up to Day 700).
- MAAEs (Section 11.2.4; Appendix 2) from Day 1 throughout the entire study duration (up to Day 700).
- SAEs and AESIs (Section 11.2.2; Appendix 2) from Day 1 throughout the entire study duration (up to Day 700).
- Physical examination findings (Section 8.5.3).
- Vital sign measurements (Section 8.5.4).

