8.5.2. Safety Telephone Calls

A safety telephone call is a telephone call made to the participant by trained site personnel. This call will follow a script, which will facilitate the collection of relevant safety information. The participant will be interviewed according to the script, and information will be collected about the occurrence of any MAAEs, SAEs, AESIs, or AEs leading to study withdrawal, concomitant medications associated with those events, and any nonstudy vaccinations.

The timing of the safety telephone calls is provided in Table 1.

All safety information described by the participant must be documented in source documents and not documented on the script used for the safety telephone contact.

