8.6.1. Time Period and Frequency for Collecting AE and SAE Information

Medical occurrences that begin before the first vaccination with mRNA-1893 but after obtaining informed consent will be recorded in the Medical History/Current Medical Conditions section of the eCRF, not in the AE section; however, if the condition worsens at any time during the study, it will be recorded and reported as an AE.

The time periods for collection, recording, and reporting of solicited ARs, unsolicited AEs, and SAEs are found in Appendix 2.

Adverse events may be collected as follows:

• Observing the participant.

Receiving an unsolicited complaint from the participant.

• Questioning the participant in an unbiased and nonleading manner.

Solicited ARs will be collected from the day of injection through 6 days after each IP injection (Days 1 through 7 and Days 29 through 35). Other (unsolicited) AEs will be collected from the day of injection through 28 days after each IP injection (Days 1 through 29 and Days 29 through 57).

Serious AEs will be collected from the first IP injection until the last follow-up visit after the last IP injection at the time points specified in the SOAs (Table 1 and Table 2).

All SAEs will be recorded and reported to the Sponsor or designee immediately, and under no circumstance should this exceed 24 hours, as indicated in Section 11.2.11. The investigator will submit any updated SAE data to the Sponsor within 24 hours of it being available.

An abnormal value or result from a clinical or laboratory evaluation (eg, a radiograph, an ultrasound, or an electrocardiogram) can also indicate an AE if it is determined by the investigator to be clinically significant (eg, leads to dose modification or study drug discontinuation or meets any serious criteria). If this is the case, it must be recorded in the source document and as an AE on the appropriate AE page of the eCRF. The evaluation that produced the value or result should be repeated until that value or result returns to normal or is stabilized and the participant's safety is not at risk.

Investigators are not obligated to actively seek AEs or SAEs after conclusion of the study participation. However, if the investigator learns of any SAE, including a death, at any time after a participant has been discharged from the study, and he/she considers the event to be reasonably related to the IP or study participation, the investigator must promptly notify the Sponsor.

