For calculation regarding antibody titers/antibody concentrations, antibody values reported as below LLOQ will be replaced by 0.5 × LLOQ. Values that are greater than the upper limit of quantification (ULOQ) will be converted to the ULOQ. Missing results will not be imputed.

The following stages for safety analyses will be used in this study:

- Up to 28 days after any vaccination: this stage starts at the day of each vaccination
 and continue through the earliest date of (the day of each vaccination and 27
 subsequent days, next vaccination [if applicable]). This analysis period will be used
 as the primary analysis period for safety analyses including unsolicited AE, except
 for solicited AR, unless specified otherwise.
- Up to 28 days after the first vaccination.
- Up to 28 days after the second vaccination.
- Overall stage: this analysis period starts at the first injection on Day 1 and continues through the earliest date of (study completion, discontinuation from the study, or death).

Unscheduled visits: Unscheduled visit measurements will be included in analysis as follows:

- In scheduled visit windows per specified visit windowing rules.
- In the derivation of baseline/last on-treatment measurements.
- In the derivation of maximum/minimum on-treatment values and maximum/minimum change from baseline values for safety analyses.
- In individual subject data listings as appropriate.

Visit windowing rules: The analysis visit windows for protocol-defined visits are provided in Appendix B.

Incomplete/missing data:

- Imputation rules for missing prior/concomitant medications, non-study vaccinations and procedures are provided in Appendix C.
- Imputation rules for missing AE dates are provided in Appendix D.
- For laboratory assessments, if majority of results are indefinite, imputation of these values will be considered. If the laboratory results are reported as below the LLOQ (e.g., <0.1), the numeric values will be imputed by 0.5 × LLOQ in the summary. If the laboratory results are reported as greater than the ULOQ (e.g., >3000), the numeric values will be imputed by ULOQ in the summary.
- Other incomplete/missing data will not be imputed, unless specified otherwise.

Treatment groups:

The following vaccination groups will be used for summary purposes:

- mRNA-1893 vaccine: μg (2-dose)
- mRNA-1893 vaccine: CCI μg (2-dose)
- mRNA-1893 vaccine: μg (single-dose)
- mRNA-1893 vaccine: Total
- Placebo

Summary by flavivirus serostatus:

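### Overall-stage tables of all unsolicited TEAEs run to study completion, but ordinary unsolicited AEs are collected systematically for only 28 days after each injection

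*SAP*

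**What the plan says.** **Analysis.** SAP 6.3.1 summarises unsolicited AEs by serostatus, vaccination group and "stage (up to 28 days after each vaccination, up to 28 days after any vaccination and overall stage". SAP 6.1 defines the last of these: "this analysis period starts at the first injection on Day 1 and continues through the earliest date of (study completion", discontinuation or death). Completion is about Day 196 without the Extension and about Day 700 with it (SAP 6.2.1, Protocol 4.6). SAP 6.1 also names the 28-day period after any vaccination "as the primary analysis period for safety analyses including unsolicited AE, except" for solicited reactions.

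SAP 6.3.1.1 to 6.3.1.4 then list tables of any or all unsolicited TEAEs: in summary, by SOC and PT, by PT, for selected SMQs and by maximum severity. None of these subsections limits an overall-stage version to particular classes of event, and the TEAE definition in SAP 6.3.1 has no end date.

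**Collection.** Protocol 8.5 lists "Unsolicited AEs observed or reported during the 28 days following each IP injection (ie, the day of injection and 27 subsequent days"). Protocol 8.6.1 gives nearly the same window: "Other (unsolicited) AEs will be collected from the day of injection through 28 days after each IP injection". MAAEs, SAEs and AESIs are recorded "from Day 1 throughout the entire study duration (up to Day 700"), and AEs leading to discontinuation also run to Day 700. At the safety calls, "information will be collected about the occurrence of any MAAEs, SAEs, AESIs, or AEs leading to study withdrawal" (Protocol 8.5.2). The Extension schedule (Protocol Table 2) has recording rows for MAAEs, SAEs and AESIs, and none for other AEs.

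**The concern.** Within the overall stage the same row label changes meaning. Inside the 28-day windows, an unsolicited TEAE is any such event the participant reports. Afterwards it is an event that was medically attended, serious, of special interest or led to discontinuation, together with whatever else a site happened to record. The resulting percentage has no clear target.

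This matters because long-term safety is a stated purpose of the follow-up (Protocol 2.2 and 4.2). An overall-stage rate, or a low SMQ count, could be read as a safety estimate through Day 196 or Day 700 when most of that time had only partial collection.

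**Working it through.** The plan states no figure for this point, so the check sets the collection window against the analysis window.

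**1. Share of the overall stage under full collection**

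- Full window: 28 days (injection day plus 27, Protocol 8.5) × 2 injections = 56 days.
- Stage ending at Day 196: 56/196 = 28.6%; the other 140 days (71.4%) have partial collection.
- Stage ending at Day 700: 56/700 = 8.0%; the other 644 days (92.0%) have partial collection.
- Taking Protocol 8.6.1 literally (Days 1 to 57) barely changes this: 57/196 = 29.1% and 57/700 = 8.1%.

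These are shares of calendar time. They are not the size of a bias.

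**2. What the cumulative percentage estimates**

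Let *h* be a constant rate of ordinary AEs per day, *T* the stage length, and *q* the share of later AEs that fall into a class still collected.

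- 28-day stages: 1 − exp(−56*h*)
- Whole-study risk: 1 − exp(−*hT*)
- Overall-stage table: 1 − exp(−*h*[56 + *q*(*T* − 56)])

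For any *q* strictly between 0 and 1, the third quantity lies strictly between the first two. It equals neither, and its position depends on *q*, which the documents do not give.

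The figures below only illustrate this ordering. The AE risk per 28 days (10% or 20%), the constant rate and *q* from 0.1 to 0.5 are assumptions, not estimates for this trial. With 10% per 28 days, *T* = 196 and *q* = 0.1, the exponent is (56 + 14)/28 = 2.5, and 1 − 0.9^2.5 = 23.2%. With full collection it is 1 − 0.9^7 = 52.2%.

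| AE risk per 28 days | Stage end | 28-day stages (any vaccination) | Overall-stage table, *q* = 0.1 / 0.3 / 0.5 | Full collection |
|---|---|---|---|---|
| 10% | Day 196 | 19.0% | 23.2% / 30.8% / 37.8% | 52.2% |
| 10% | Day 700 | 19.0% | 36.4% / 60.8% / 75.9% | 92.8% |
| 20% | Day 196 | 36.0% | 42.8% / 54.2% / 63.4% | 79.0% |
| 20% | Day 700 | 36.0% | 61.7% / 86.3% / 95.1% | 99.6% |

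**3. Which rows are exposed**

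- *Any unsolicited, treatment-related, mild and moderate:* exposed, since late events of these kinds need not fall into a class that is still collected.
- *SMQ tables:* exposed. SAP 6.3.1.3 gives hypersensitivity, angioedema, cardiac arrhythmia and autoimmune disorder among its examples. The AESI list (Protocol Table 15) covers thrombocytopenia, named neurologic diseases, anaphylaxis and myocarditis/pericarditis. A late SMQ event outside that list is caught only through another collected class or as a significant finding at a visit.
- *Severe:* least exposed. Protocol 11.2.8 defines a severe unsolicited AE as one that both stops daily activity and needs intensive treatment, so most should be MAAEs or SAEs.
- *SAEs, AESIs, MAAEs, discontinuations:* not exposed, as they are collected throughout.

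The SMQ and severity subsections name no stage. They reach the overall stage through the general sentence in SAP 6.3.1.

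**The case against.** The strongest reply is that the headline analysis is sound. SAP 6.1 makes the 28-day stage primary for unsolicited AEs, which matches the primary endpoint in SAP 3.1. Long-term classes have their own rows and tables, so nobody needs the any-unsolicited row to judge late safety. All of that stands, and it confines the point to secondary descriptive tables.

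Collection after Day 57 is also not nil. Protocol 8.5.3 requires significant new findings after consent to go on the AE page, with no day limit, and clinically significant findings at study visits to be reported as MAAEs. Clinic visits continue to Day 700. This narrows the gap but does not restore systematic questioning for ordinary AEs. The table shells might restrict these tables, but they are not among the documents and the SAP text sets no such limit.

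A reader might infer more than the documents support:

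- *That the overall tables would show AE frequency collapsing after Day 57.* They would not. The overall stage is cumulative from Day 1, so its percentage cannot fall below the 28-day figure. No stage in SAP 6.1 starts after Day 57; the CSR addendum carries data from Month 8, but the SAP defines no separate AE stage for it.
- *That late reporting falls by a known amount.* Any such amount would simply restate the assumed share of events that are medically attended.
- *That comparisons between arms are biased.* Collection rules are the same in every arm, assessors are blinded (Protocol 6.3.2) and no hypothesis is tested (SAP 4.2).

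**Conclusion.** The mismatch is real, though limited in reach. Followed as written, the SAP yields overall-stage percentages for any unsolicited, treatment-related, mild or moderate, and SMQ-selected TEAEs that rest on full collection for 29% of a 196-day stage or 8% of a 700-day stage. They under-ascertain late events and have no clear interpretation as either a 28-day or a whole-study risk.

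The time shares assume two injections and follow-up to the stated end. How far any given percentage falls short cannot be computed from the documents. The damage is to the meaning of absolute rates; the primary safety conclusions and the comparison with placebo stand. This is a worthwhile, cheap improvement.

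**What to change.** In SAP 6.3.1:

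1. Produce the all-unsolicited, treatment-related, severe, by-severity and SMQ tables for the 28-day stages.
2. For the overall stage, restrict them to events that are SAEs, AESIs, MAAEs, AEs leading to discontinuation or deaths. AEs leading to discontinuation must be kept, since they are collected throughout and need not belong to another class.
3. Add a footnote to the overall-stage tables giving the collection window for each class.
4. Keep other AEs recorded after the 28-day windows in the listings.

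The cost is SAP wording and table shells; data collection does not change. The downside is that minor AEs recorded incidentally after the 28-day windows appear only in listings.
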